Handling of prior and concomitant medications missing data is described in the [Section 4.2.2](#).

6.8.2 Tables

For non-AEDs, tables are sorted alphabetically by Anatomical Main group (ATC level 1) and Pharmacological Subgroup (ATC level 3) and within level 3 by descending frequency of PT in the all subjects group.

For AEDs, tables are sorted alphabetically by Chemical Subgroup (ATC level 4) and within level 4 by descending frequency of preferred term in the all subjects group.

The following tables will be provided:

- Past Anti-Epileptic Drugs
- Concomitant Anti-Epileptic Drugs
- Anti-Epileptic Drugs at Study Visit 1
- Past Medications (Non-AEDs)
- Concomitant Medications (Non-AEDs)

6.8.3 Listings

A listing Medication Glossary represents the mapping of reported terms to preferred terms and WHO-DD coding.

- Anatomical Main Group, Level 1
- Pharmacological Subgroup, Level 3
- Preferred Term
- Reported Term
- AED Flag

A subject data listing Past and Concomitant Medications (Non AEDs) presents for subjects on adjunctive therapy and for subjects on monotherapy, separately:

- Age Category
- Site/Subject Number
- Anatomical Main Group (Level 1)/Pharmacological Subgroup (Level 3)/Preferred Term/Reported Term
- Dose per Intake and Unit
- Frequency/Formulation
- Indication
- Past / Concomitant medication
- Start Date (Relative Day)/Stop Date (Relative Day)

This listing is repeated for:

- Concomitant Anti-Epileptic Drugs

- Changes in Concomitant AEDs – AEDs that started on or after First Dose of Study Medication

A subject data listing Past Anti-Epileptic Drugs presents for subjects on adjunctive therapy and for subjects on monotherapy, separately:

- Age Category
- Site/Subject Number
- Anatomical Main Group (Level 1)/Pharmacological Subgroup (Level 3)/Preferred Term/Reported Term
- Maximum Daily Dose and Unit
- Start Date (Relative Day)/Stop Date (Relative Day)
- Reason for Discontinuation

7 MEASUREMENTS OF TREATMENT COMPLIANCE

Summary tables and listings will be presented for subjects on adjunctive therapy and for subjects on monotherapy, separately.

7.1 Definitions and Derivations

Since derivations for compliance is connected to derivations for exposure, derivation to both topics are described here.

Date of first dose of study medication is documented in the “First Administration” CRF.

Missing values for date of last administration of study medication are imputed as specified in [Section 4.2.4](#).

Details on study medication administration are recorded on the CRFs: First Administration; Study Medication Administration – Dry Syrup; and Study Medication Administration – IV.

Overall compliance with Levetiracetam, administered once in the morning and once in the evening, will be examined for subjects whose total study medication administration and first and last days of treatment in the first and/or second period are known:

- First Period, Treatment compliance (%) will be calculated as follows:

$$\text{Compliance (\%)} = \frac{\sum_{\text{first day}}^{\text{last day}} (\text{\# of actual administrations per day})}{\text{total \# of administrations planned during the first period}} \times 100$$

where “total # of administrations planned during the first period” is equal to the total number of administrations planned during first administration of study medication to last planned administration in Evaluation Period, or day of discontinuation, which will be calculated as the duration of Evaluation Period in days $\times 2$. In consideration of whether the first administration is taken in the morning or in the evening, please see [Section 10.1.1](#).

- Second Period, Treatment compliance (%) will be calculated as follows:

$$\text{Compliance (\%)} = \frac{\sum_{\text{first day}}^{\text{last day}} (\text{\# of actual administrations per day})}{\text{total \# of administrations planned during the time the subject was in second period}} \times 100$$

where “total # of administrations planned during the time the subject was in the second period” is equal to the total number of administrations planned during first planned administration of study medication and last planned administration in Maintenance Period, or day of discontinuation, which will be calculated as the duration of Maintenance Period in days $\times 2$. In consideration of whether the first administration is taken in the morning or in the evening, please see Section 10.1.1.

- Overall Period, Treatment compliance (%) will be calculated as follows:

$$\text{Compliance (\%)} = \frac{\sum_{\text{first day}}^{\text{last day}} (\text{\# of actual administrations per day})}{\text{total \# of administrations planned during the time the subject was in the study}} \times 100$$

where “total # of administrations planned during the time the subject was in the study” is equal to the total number of administrations planned during first planned administration of study medication and last planned administration, or day of discontinuation which will be calculated as the duration of exposure to study medication in days $\times 2$. In consideration of whether the first administration is taken in the morning or in the evening, please see Section 10.1.1.

Percent overall compliance for study medication will be summarized for the Evaluation and Maintenance Period in two ways:

- Descriptive statistics will be presented by age category and overall.
- Percent compliance data will be summarized by age category and overall, and will be categorized according to the following categories:
 - < 80%
 - 80 – 120%
 - > 120%.

Summary statistics will be based on the SS_A and SS_M.

7.2 Tables

A table Study Medication Compliance presents for subjects on adjunctive therapy and for subjects on monotherapy, separately:

- Summary statistics on compliance
- Frequency distribution (<80%, 80-120%, >120%).

7.3 Listings

A subject data listing Study Medication Compliance presents for subjects on adjunctive therapy and for subjects on monotherapy, separately:

- Age Category
- Site/Subject Number
- Period
- Formulation (IV or Dry Syrup)
- Number of administrations
- Target number of administrations
- Study Medication Compliance (%)

8 EFFICACY ANALYSES

Summary tables and listings will be presented for subjects on adjunctive therapy and for subjects on monotherapy, separately.

Descriptive statistics (n, mean, SD, median, Q1, Q3, minimum, and maximum) will be calculated for the continuous secondary efficacy variables and absolute and relative frequencies will be calculated for the categorical efficacy variables.

The primary efficacy variable and potentially the two secondary efficacy variables will be compared with a threshold in a confirmatory way according to the hierarchical testing procedure (see Section 4.5). All efficacy variables which are not tested as confirmatory in the course of the hierarchical testing procedure will be analyzed exploratively only. Descriptive summaries will be created for all these variables irrespective of this.

8.1 Statistical Analysis of the Primary Efficacy Variable

8.1.1 Primary Efficacy Variable for Adjunctive Therapy

First Period

The primary efficacy variable for subjects on adjunctive therapy for the First Period is the percent reduction in partial seizure frequency per week from Baseline to Study Visit 6. In order to include the EEG failures subjects who were enrolled prior to Protocol Amendment 3, analysis visit will be used therefore the primary efficacy variable is presented as the percent reduction in partial seizure frequency per week from Baseline to Analysis Visit 3.

The percent reduction in partial seizures per week from Baseline to Study Visit 6 (Analysis Visit 3) will be calculated as:

$$\frac{\text{Number of partial seizures per week at Baseline} - \text{Number of seizures per week at Analysis Visit 3}}{\text{Number of partial seizures per week at Baseline}} \times 100$$

The number of partial seizures per week at Baseline will be based on the Retrospective Baseline seizure counts (during the 2 weeks prior to Study Visit 1) + Selection Period (Study Visit 1 and Study Visit 2*), see Section 3.3, and will be calculated as:

[total number of partial seizures entered on the DRC starting at the 2 weeks prior to Study Visit 1 until Study Visit 3 divided by the number of days on which data was entered on the DRC] $\times 7$.

*Study Visit 2 is only applicable for those subjects enrolled prior to Protocol Amendment 3.

The number of seizures per week at Study Visit 6 (Analysis Visit 3) will be based on the seizure count from Analysis Visit 2 to Analysis Visit 3 and will be calculated as:

[total number of partial seizures entered on the DRC during the period starting 1 day after Study Visit 5 (Analysis Visit 2) through Study Visit 6 (Analysis Visit 3) divided by the number of days, within this period, on which data was entered on the DRC] $\times 7$

Those seizure free days (ie, seizure count is 0 and there is no entry of DRC data) will be included into denominator. Data was NOT entered on DRC only refer to the situation that “Not Done” was ticked on CRF “Seizure Count” page

Descriptive statistics (n, mean, standard deviation, median, Q1, Q3, minimum, and maximum) will be calculated for the percent reduction in partial seizure frequency per week from Study Visit 6 (Analysis Visit 3) by Baseline age category (3 categories: 1 month to <1 year, 1 year to <2 years, and 2 years to <4 years), and for all subjects combined (overall). The corresponding 95% CI for the median percent reduction at Study Visit 6 (Analysis Visit 3) will be provided by age category and overall. The 95% CI will be derived from a distribution-free method based on order statistics. For example, under the assumption that data does not follow a Gaussian distribution the 95% CI might be calculated by using the UNIVARIATE procedure from SAS® with ciquantdf (alpha=.05) as specification ^[1]. If the lower limit of the 95% confidence interval for overall is greater than the predefined threshold of 15.0%, the efficacy of LEV is shown significant. If this test shows a significant result, then it will be repeated for the corresponding Study Visit 4 (Analysis Visit 1) and Study Visit 5 (Analysis Visit 2) variable hierarchically (see Section 8.2.1). In that case, the second and the third test is also regarded as confirmatory as due to the hierarchical testing procedure no alpha adjustment is needed (see Section 4.5).

A summary table based on the FAS_A will be presented:

- Percent Reduction in Partial Seizure Frequency per Week from Baseline to Visit 6 (Analysis Visit 3), by Age Category, Adjunctive Therapy Subjects

Combined First and Second Periods

There is no primary efficacy variable for subjects on adjunctive therapy for the combined First and Second Periods.

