3.4 Protocol Deviations

After all CRFs have been retrieved and entered, all queries issued and answered to the extent possible, and prior to locking the database, a final Data Evaluation Meeting (DEM) will be held.

The meeting covers but is not limited to the following tasks:

- Review and assessment of important protocol deviations
- Agreement/confirmation of data handling rules
- Evaluation of statistical methodology

Important protocol deviations are to be classified into important for:

- Efficacy
- Conduct/Patient Management

Criteria and rules for the identification and classification of important protocol deviations regarding their impact on study conduct/subject handling and/or the assessment of efficacy are to be setup and to be minuted. Decisions made during the meeting are minuted.

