4.2 Handling of Dropouts or Missing Data

Days with missing seizure data will not be used for the calculation of seizure frequency per week. If subjects drop out, their seizure counts over the available period will be used and transformed into seizure frequency per week, by dividing the number of seizures during the available period by the number of days of that period, multiplied by 7.

Safety variables will be analyzed insofar as they are available, without imputation or carrying values forward.

Imputations for missing or partial values for dates for AEs and concomitant medications will be applied to determine if an event is to be considered treatment-emergent or concomitant. Across safety and PK analyses, only reported data will be used.

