8.1.3 Sensitivity Analyses of the Primary Efficacy Variable

For the subjects who have important protocol deviations who are considered with impact on efficacy, BLOCF (Baseline Observation Carried Forward) will be applied for the post-baseline value.

A summary table based on the FAS_A will be presented:

- Percent Reduction in Partial Seizure Frequency per Week from Baseline to Visit 6 (Analysis Visit 3), by Age Category, Adjunctive Therapy Subjects, (BLOCF)

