Number of partial seizure frequency per week, as collected on the DRC, is calculated at Analysis Visit x, x=1, 2, 3, 4, ..., as:

Number of partial seizures per week at Analysis Visit x = [total number of partial seizures entered on the DRC during the period starting 1 day after Analysis Visit x-1 through Study Day of Analysis Visit x divided by the number of days, within this period, on which data was entered on the DRC] x 7. Those seizure free days (i.e. seizure count is 0 and there is no entry of DRC data) will be included into denominator. Data was NOT entered on DRC only refer to the situation that “Not Done” was ticked on CRF “Seizure Count” page.

The following summary tables based on the FAS_A will be presented:

- Percent Reduction in Seizure Frequency per Week, by Analysis Visit, Adjunctive Therapy Subjects
- Percent Reduction in Seizure Frequency per Week Grouped into 6 Categories by Analysis Visit, Adjunctive Therapy Subjects

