- For each analysis visit, percent reduction in all types of seizure frequency per week from Baseline.

A table Percent Reduction in All Types of Seizure Frequency per Week during Combined First and Second Periods, Adjunctive Therapy Subjects presents summary statistics of subjects on adjunctive therapy, for each analysis visit on the FAS_A.

Note: This is combined over the age categories.

A table Percent Reduction in All Types of Seizure Frequency per Week during Combined First and Second Periods, Monotherapy Subjects presents summary statistics of subjects, on monotherapy, for each analysis visit on the FAS_M.

Note: This is combined over the age categories.

- For each analysis visit, percent reduction in all type of seizure frequency per week from Baseline grouped into 6 categories: <0%, 0% to <25%, 25% to <50%, ≥50%, ≥75%, and 100%.

A table Percent Reduction in All Types of Seizure Frequency per Week Grouped into 6 Categories During Combined First and Second Periods, Adjunctive Therapy Subjects, presents the number and percentage of subjects on adjunctive therapy within each of the above defined six categories for all analysis visits on the FAS_A.

Note: This is combined over the age categories.

A table Percent Reduction in All Types of Seizure Frequency per Week Grouped into 6 Categories During Combined First and Second Periods, Monotherapy Subjects, presents the number and percentage of subjects on monotherapy within each of the above defined six categories for all analysis visits on the FAS_M.

Note: This is combined over the age categories.

The following other efficacy variable is only applicable to Monotherapy:

- Percent of subjects who are continuously 6-months seizure-free monitored by the patient diary.

A subject is considered 6-months seizure free if they are seizure free for at least $26 \times 7 = 182$ consecutive days during the combined period of Evaluation Period + Dose adjustment Period + Maintenance Period, otherwise they are not considered seizure free.

The seizure free time interval must not contain days for which seizure data are missing, ie, “Not done” was checked on the Seizure Count CRF or seizure information is missing otherwise, eg because the complete and required CRF module was not filled out for a certain visit.

Subjects who received less than 182 days study medication are counted as not having achieved 6-months seizure freedom.

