Missing seizure dates and dates for “not done” rows (in the following both are called “row”) are handled as follows:

- If the row date is missing completely (no entry), two cases can occur

1. The missing row date is in the first row of the CRF.
In this case, the visit date of the visit before the documentation visit is imputed.
2. The missing row date is not the first row of the CRF.
In this case, the date of the day after the last entry in the rows before the row with the missing date is imputed.

- If the row date is missing completely (“UNK”, ie, unknown), then the date of the visit before the documentation visit is imputed, independent of the row being the first row or a later one.
- If the year and month of a row date is present but the day is missing, then the same imputation as for a completely missing row date is performed first. If the imputed date is before the first of the month that is documented, then the first day of the month is used.
- If the year of a row date is present but the month is missing, then the same imputation as for a completely missing date is performed first. If the imputed date is before the first of the year that is documented, then the first day of the year is used.

A table Percent and Number of Subjects Who are continuously 6-Months Seizure-Free Monitored by Patient Diary During the Evaluation, Dose-adjustment and Maintenance Period presents the number and percentage of subject on monotherapy who are continuously 6-months seizure-free on the FAS_M.

Note: This is combined over the age categories.

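### The primary endpoint counts a never-completed Seizure Count module as a seizure-free interval, so a child with no Visit 6 seizure data scores a 100% reduction

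*SAP*

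**What the plan says.** The general rule, in SAP 4.2 and in the same words in Protocol 13.7, is: "Days with missing seizure data will not be used for the calculation of seizure frequency per week". Neither section defines a missing day.

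SAP 8.1.1 supplies a definition for the primary variable. The weekly rate is the diary seizure count divided by the number of days with diary data, times 7. It then adds: "Those seizure free days (ie, seizure count is 0 and there is no entry of DRC data) will be included into denominator", followed by: "Data was NOT entered on DRC only refer to the situation that “Not Done” was ticked on CRF “Seizure Count” page". SAP 8.2.1 repeats both sentences for each analysis visit.

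SAP 8.3.2, for continuous 6-month seizure freedom in monotherapy, uses a wider definition. A day is missing if the *Not Done* box was checked, or if "seizure information is missing otherwise, eg because the complete and required CRF module was not filled out for a certain visit". The same section sets rules for "Missing seizure dates and dates for “not done” rows", which suggests that the page holds dated seizure rows and not-done rows, with no row for a seizure-free day.

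The only sensitivity analysis of the primary variable (SAP 8.1.3) carries the baseline forward: "For the subjects who have important protocol deviations who are considered with impact on efficacy".

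**The concern.** If seizure-free days generate no row, a day without a row inside a completed module can reasonably mean zero seizures. That convention is not disputed. The difficulty is the module that was never filled out and carries no tick. The rule in 8.1.1 cannot tell it apart from a module completed for a child who had no seizures, and it resolves the doubt in favour of zero.

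At Visit 6 a child with no seizure data would then enter the primary test as a complete responder against the 15% threshold. The same applies at Visits 4 and 5, which become confirmatory if the hierarchy is passed. The child stays in the analysis, because FAS_A requires only one post-baseline efficacy assessment at any time. At baseline the rule works the other way: a blank Selection Period module adds days but no seizures, which understates the baseline rate.

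The SAP thus handles one kind of missing data in two ways. The stricter handling protects an *other* variable and the looser one governs the confirmatory endpoint. SAP 3.9 declares no change to protocol-defined analyses, so the narrowing is not explained.

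**Working it through.** **The plan's own figures.** SAP 2.4 gives 34 evaluable subjects and 10% non-evaluable: 34 / 0.90 = 37.8, rounded up to 38. This reproduces and is not in dispute. The 90% and ≥80% powers come from resampling data of study N01009, which the documents do not contain, so they cannot be reproduced.

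**One child at Visit 6.** The interval runs from the day after Visit 5 through Visit 6, nominally 14 days (SAP 8.1.1; Weeks 4 to 6). With a blank, unticked module:

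- rate = 0 / 14 × 7 = 0 seizures per week
- reduction = (B − 0) / B × 100 = 100% for any baseline B above 0

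Under the 8.3.2 definition the interval has no valid days, so the child has no Visit 6 value.

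**The success rule as a count.** SAP 8.1.1 uses the order-statistic 95% confidence interval of the median and requires its lower limit to exceed 15%. The lower limit is the l-th smallest value, with l the largest integer for which P(Bin(n, 0.5) ≤ l − 1) ≤ 0.025. At n = 38, l = 13 (coverage 96.6%), so success needs at least 38 − 13 + 1 = 26 children above 15%.

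**Chance of success when the true median is exactly 15%.** Let k be the number of blank Visit 6 modules, assumed unrelated to outcome. Under the current rule k children are certain to lie above 15%, so the chance is P(Bin(38 − k, 0.5) ≥ 26 − k). If they are treated as missing, the interval is recomputed at n = 38 − k.

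| k | Current rule | Treated as missing |
|---|---|---|
| 0 | 26 of 38: 0.0168 | 26 of 38: 0.0168 |
| 1 | 25 of 37: 0.0235 | 25 of 37: 0.0235 |
| 2 | 24 of 36: 0.0326 | 25 of 36: 0.0144 |
| 3 | 23 of 35: 0.0448 | 24 of 35: 0.0205 |

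At k = 1 the two rules happen to require the same count. From k = 2 the current rule exceeds 0.025 and the alternative does not.

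**Baseline, opposite direction.** The baseline pools the 14 retrospective days with the Selection Period, which lasts at most 9 days (Protocol 5.1.4). Suppose the Selection Period module is blank and the true daily rate r does not change on treatment:

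- recorded baseline = 14r / 23 = 0.61r per day
- apparent reduction = 1 − 23/14 = −64%, that is, a 64% increase

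With only 2 blank days the figure is 1 − 16/14 = −14%.

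**The case against.** The strongest counter-argument is textual. The inclusion sentence joins two conditions, a count of zero and no diary entry, and a module never completed has an unknown count rather than a zero. Read together with SAP 4.2 and Protocol 13.7, the text could be taken to exclude such days already. This reading does not survive the next sentence, which limits absent data to the ticked box with the word *only*. A programmer would follow that specific derivation, since the general rule defines nothing.

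A second argument is that the route is narrow. The visit must have taken place, a required page must be blank, the box unticked, the query unresolved, and the data evaluation meeting (SAP 3.4), whose tasks include confirming data handling rules, must not have dealt with it. This stands as far as frequency goes. But queries are closed only in the sense of "all queries issued and answered to the extent possible", and no section says what happens to an interval that stays blank. Baseline carried forward would catch it only if it had been classed as an efficacy-relevant important deviation, and the specification that decides this is not among the documents.

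Third, a stricter rule is natural for an unbroken 182-day seizure-free run, where a single unknown day defeats the claim. That explains why 8.3.2 is careful, but it does not justify scoring unknown intervals as zero in the primary test.

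Fair limits on the size also stand: one blank module makes no difference to the error rate, the calculation sits exactly at the 15% boundary, and the 64% figure uses the longest permitted Selection Period.

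**Conclusion.** The concern holds. SAP 8.1.1 and 8.2.1 state a rule that, applied as written, turns an absent Visit 6 record into a complete response, and this conflicts with SAP 8.3.2 and with the general exclusion of missing days. In the illustration, the chance of a false success rises from 1.7% to 3.3% with two such children and 4.5% with three, against 1.4% and 2.0% if they are treated as missing.

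These figures assume n = 38, a true median of exactly 15%, and blank modules unrelated to outcome. The documents do not say how many blank modules to expect, and the number may be zero. The point should be fixed because the confirmatory test is small enough for two cases to matter and the SAP already contains the better definition.

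**What to change.** In SAP 8.1.1 and 8.2.1, replace the *Not Done*-only definition with that of 8.3.2, for baseline and post-baseline alike. State the convention openly: a day without a row counts as zero seizures only if the module for that interval was completed and the day is not marked *Not Done*; days in an interval with an unfilled module are missing. State also that a child with no valid days in the Visit 6 interval has no Visit 6 value. Query every interval without a completed module before the snapshot, and report the current rule as a sensitivity analysis.

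The cost is a few sentences in the SAP and one query check. Some children will have fewer evaluable days or no Visit 6 value, so n may fall below 38, whereas the ≥80% power in SAP 2.4 assumes no non-evaluable subjects. As a guide, suppose 73.1% of children truly exceed 15%, the share that gives exactly 80% power at n = 38. Losing one, two or three children then gives 82.8%, 75.7% or 79.0%; the figures are uneven because the required count moves in whole subjects.
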